Sample size	
382 patients
 
191 control arm (SRS)
 
191 investigational arm (FSRT)
										
Randomization	
1 (control arm): 1 (experimental arm)
 
Randomization will be conducted at the patient level.
										
Treatment	
Control arm: Single-fraction stereotactic radiosurgery (SRS) with a total dose of 1×24 Gy (\varnothing 1-2 cm), 1×18 Gy (\varnothing 2-3 cm) or 1×15 Gy (\varnothing 3-4 cm), respectively, delivered to the metastasis according to RTOG 9005 guidelines (gold standard) including a margin of up to 1 mm depending on institution-specific accuracy.
 
Experimental arm: Fractionated stereotactic radiotherapy (FSRT) with a total dose of 48 Gy in 12 fractions of 4 Gy each, with a safety margin of 2 mm
										
Follow-up	
Until 2 years after treatment
 
Initially, 6 weeks and 3 months after completion of radiotherapy (for detection of early treatment failure), then once every 3 months. Follow-up is performed for progression/radionecrosis as well as for overall survival, toxicity and distant progression, respectively.
										
Financing	
This study is funded by the German Cancer Aid (Deutsche Krebshilfe, 70113619) and is partly financed by Universitätsklinikum Erlangen (University Hospital of Erlangen).
										

FSRT TRIAL STUDY FLOW CHART

FSRT TRIAL EXAMINATION SCHEDULE

[figure not shown]
Assessment	Screening	Last RT	Time after completion of radiotherapy (RT)								
	≤ 4 weeks before the start of RT		6 weeks	3 months	6 months	9 months	12 months	15 months	18 months	21 months	24 months
MRI	• ^{a)}		•	•	•	•	•	•	•	•	•
ECOG / KPS	•	•	•	•	•	•	•	•	•	•	•
Toxicity according to NCI CTCAE v. 5.0	•	•	•	•	•	•	•	•	•	•	•
EORTC QLQ-C30	•	•	•	•	•	•	•	•	•	•	•
EORTC QLQ-BN20	•	•	•	•	•	•	•	•	•	•	•
Documentation of glucocorticoid dose	•	•	•	•	•	•	•	•	•	•	•
Documentation of systemic treatment	•	•	•	•	•	•	•	•	•	•	•
Assessment of RPA and GPA score	•										
Informed Consent	•										
Pregnancy test ^{b)}	•										
Planning CT	•										
Blood sample for translational research	•		•		•						

a) Time from MRI to start of radiotherapy has to be ≤ 14 days

b) In females of childbearing potential: Serum β-HCG
If one follow-up examination is delayed, the date of the next follow-up examination should not be postponed but should be conducted at the specific prespecified date following radiotherapy.

FSRT TRIAL ALGORITHM IN CASE OF AN ENLARGING LESION

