5.1. Schedule of examinations and procedures

5.1.1. Screening examinations before treatment

1. Magnetic resonance imaging (MRI) of the brain

Note: Time from MRI to start of radiotherapy has to be ≤ 14 days

2. Performance status assessment

ECOG / KPS

**3. Assessment of Adverse Events before treatment
(Medical history relevant for the study)**

NCI CTCAE v5.0

4. Assessment of Quality of Life

EORTC QLQ-C30

EORTC QLQ-BN20

5. Assessment of RPA and GPA prognostic scores

6. Documentation of glucocorticoid dose

**7. Documentation of systemic treatment including prior
systemic therapies**

8. Written informed consent

9. Pregnancy test in women of childbearing potential

Pregnancy should be ruled out by determining Serum β -HCG

10. Planning CT

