9.2. Sample size calculation

On the basis of available retrospective and dose-response relationship data, it is expected that SRS will result in a 12-month local tumor control rate of approximately 65% and that FSRT can increase this rate to about 80% (cf. Section 1.4). This difference is considered to be clinically significant. A sample size of N=191 evaluable cases each in the experimental and control arm, respectively, corresponding to a total of 382 patients, is required to detect a significant difference i.e. an increase in TTLP at least this large at 12-month follow-up in a randomized comparison. The number of TTLP events to be observed is 82. This calculation is based on the following framework conditions:

- The risk of making a false claim of superiority of FSRT which actually does not exist is 2.5% (α error, one-sided).
- The success rate for identifying superiority of FSRT over the control arm which actually exists is 80% (power, $1-\beta$ error).
- Assuming an exponential decline of TTLP curves
- As this is a basically palliative setting with disseminated disease, it must be considered that about half of the patients will be dead at 12-month follow-up. Consequently, a considerable proportion of patients

will have a truncated follow-up in which no event related to the primary endpoint occurs. The extent of this quasi-drop-out process is estimated to be $\leq 50\%$ and is also assumed to be exponentially distributed over the 12 months.

- Duration of follow-up for all patients: at least 12 months or until the incidence of local progression.

Note: Due to patient entry kinetics during the planned recruitment, and due to the intended follow-up period of up to 24 months for each patient (cf. section 5.1.4), the follow-up periods for a considerably number of patients, mainly those randomized early, may be significantly longer than 12 months by the end of the study. This should result in an increase in the expected number of observed events, leading to a further increase in power of the study. Since this effect is difficult to quantify (especially due to death as a competing risk event), it is not taken into account in sample size calculation, to be on the safe side. Therefore, the recruitment period is not included among the parameters provided above.

Sample size estimates were calculated based on the method of LACHIN and FOULKES (Lachin et al. 1986), applying the software NSURV (idv, Gauting, Germany).

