9.4. Statistical analysis

Descriptive statistics will be used to check the balance of the treatment groups of the study population with regard to demographic and prognostic baseline data. Sensitivity analyses will be conducted if needed to adjust for relevant imbalances in the study population by appropriate modeling or stratification, including the corresponding co-variables. Adjusted and non-adjusted analyses will be compared and critically analyzed. With respect to the primary endpoint, the main analysis will account for the stratified randomization (stratified log-rank test).

Confirmatory analysis of the primary endpoint variable will be performed using a p-value of $p \leq 0.025$ (one-sided) as significance level.

All other parameters will be analyzed by descriptive statistics describing their frequencies, arithmetic means, standard deviations, median values, interquartile distances, ranges and, eventually, confidence intervals. If exploratory statistical analyses are performed for comparison of the different treatment arms or subgroups, p-values will be explicitly reported. As a rule, adjustment of significance levels for multiple analyses (multiplicity adjustment) will not be performed, so the p-values are considered to be descriptive and reflect a Type I error for the individual comparison and not for the overall experiment. Unless otherwise stated, two-sided tests will be used. The statistical methods listed below are usually suitable for the data and distributions expected in such studies. Their suitability will be assessed after data collection. If necessary, the choice of methods will be modified accordingly, and the respective results will be critically evaluated in a sensitivity analysis.

Toxicity and response rates as well as survival and progression-free survival rates at the specified time points will be calculated together with their exact confidence intervals and compared by either Fisher's Exact Test, the χ^2 Test or the Mantel-Haenszel test (Cochran-Armitage trend test), as appropriate for the type and extent of the variable.

The Wilcoxon-Mann-Whitney test will be used to test continuous data or scales in intergroup comparisons, and the Wilcoxon signed-rank test will be used to compare paired samples between different sampling times.

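### The only between-arm test named for scales takes no baseline score, which costs precision in the descriptive quality-of-life comparisons (minor)

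*Protocol*

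**What the plan says.** Quality of life by EORTC QLQ-C30 and QLQ-BN20 is a secondary objective (section 1.6.2). The screening list in section 5.1.1 includes "4. Assessment of Quality of Life". The examination schedule repeats both questionnaires at ten later time points: last radiotherapy, 6 weeks, and every 3 months from 3 to 24 months.

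Section 9.4 contains no analysis specific to quality of life. For data of this type it says: "The Wilcoxon-Mann-Whitney test will be used to test continuous data or scales in intergroup comparisons". Paired comparisons between time points go to the Wilcoxon signed-rank test, which addresses change over time and not the difference between arms. The regression named in that section is Cox regression, for time-to-event data.

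Four further statements in section 9.4 bear on the point:

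- Everything except the primary endpoint is analysed descriptively, and any between-arm p-values are exploratory.
- Covariate adjustment is foreseen as a sensitivity analysis, triggered by relevant baseline imbalance.
- The suitability of the listed methods is to be judged after data collection, and the choice may then change.
- Further detail is left to a statistical analysis plan.

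On mortality, section 9.2 expects that "about half of the patients will be dead at 12-month follow-up".

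**The concern.** A patient's baseline quality-of-life score usually predicts the later score. If it is left out of the comparison, the variation it explains stays in the error term and the confidence interval is wider than the collected data require.

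The route to adjustment in section 9.4 does not cure this, because it depends on seeing imbalance. A prognostic baseline improves precision even when the arms are perfectly balanced, so imbalance is the wrong trigger. Settling the method after data collection is also weaker than naming it now, since this is an open trial and the outcome is patient-reported.

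What is at stake is the width of the interval around a secondary, descriptive treatment difference. It matters most at later visits, where few patients remain.

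**Working it through.** **Inputs from the protocol**

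- Size: "A sample size of N=191 evaluable cases each in the experimental and control arm" (section 9.2), allocated 1:1.
- Primary-endpoint assumptions: 12-month local control of 65% and 80%, one-sided α of 2.5%, 80% power, 12 months of follow-up.
- Mortality of about 50% at 12 months, taken as exponential.

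**Assumptions not in the protocol**

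- ρ of 0.3, 0.5 or 0.7.
- A true arm difference of 0.3 SD, two-sided 5% tests and normally distributed scores.
- Every survivor completes the questionnaire.

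**Step 1. The plan's own figure.** The protocol states no power or sample size for quality of life, so the only figure to reproduce is 191 per arm. It confirms that the mortality assumption is read correctly.

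- Yearly hazards: λ₁ = −ln 0.65 = 0.4308, λ₂ = −ln 0.80 = 0.2231, mean λ̄ = 0.3270, loss η = ln 2 = 0.6931.
- Event probability over one year: P(λ) = λ/(λ+η) × [1 − exp(−(λ+η))] = 0.2587, 0.1461 and 0.2050 for λ₁, λ₂ and λ̄.
- Variance terms: φ = λ²/P = 0.7173, 0.3408 and 0.5216.
- Total N = [1.96 √(4 × 0.5216) + 0.8416 √(2 × 0.7173 + 2 × 0.3408)]² / (0.4308 − 0.2231)² = (2.831 + 1.224)² / 0.0431 = 381.5.

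That is 190.7, so 191 per arm. The stated size reproduces.

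**Step 2. Patients available.** Expected survivors per arm are 191 × 0.5^(t/12): about 161 at 3 months, 135 at 6, 96 at 12 and, if the same hazard continues, 48 at 24.

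**Step 3. Effect of baseline adjustment.** Relative to an unadjusted comparison of follow-up scores, the variance factor is 1 − ρ² for ANCOVA and 2(1 − ρ) for change from baseline. The equivalent gain in patients from ANCOVA is 1/(1 − ρ²) − 1.

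| ρ | ANCOVA factor | Equivalent extra patients | Change-score factor |
|---|---|---|---|
| 0.3 | 0.91 | 10% | 1.40 |
| 0.5 | 0.75 | 33% | 1.00 |
| 0.7 | 0.51 | 96% | 0.60 |

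Under normality the rank test has efficiency 0.955 relative to a normal-theory test, a further loss of about 5%.

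**Step 4. Illustrative power.** Power ≈ Φ(0.3/√v × √(n/2) − 1.96), where v is the variance factor and n is multiplied by 0.955 for a rank test.

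| Visit (n per arm) | Rank test, follow-up score | Rank test, change (ρ = 0.3 / 0.5 / 0.7) | ANCOVA (ρ = 0.3 / 0.5 / 0.7) |
|---|---|---|---|
| 3 months (161) | 75% | 60 / 75 / 92% | 81 / 87 / 96% |
| 12 months (96) | 53% | 40 / 53 / 75% | 59 / 67 / 83% |

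Simulation with 3,000 trials per setting agrees to within about two percentage points. At 3 months it gave 73–74% for the rank test on follow-up scores, and 80 / 86 / 97% for ANCOVA.

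**The case against.** The case against is substantial, and most of it limits the point without removing it.

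**The sentence does not name quality of life.** A reader might infer that the protocol has decided to compare raw scores visit by visit without baseline. It has not: the wording is generic and leaves open whether scores or changes are ranked. What stands is that no other between-arm method for scales is named. Ranking change scores would use the baseline, but since 1 − ρ² = (1 − ρ)(1 + ρ) is below 2(1 − ρ) for every ρ below 1, it stays less efficient than ANCOVA. At ρ = 0.3 it is worse than ranking the follow-up score.

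**The detail may be in the analysis plan.** Model terms and handling of missing forms commonly are, and their absence from the protocol is no finding. The point here concerns a method that the protocol does state.

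**Nothing confirmatory depends on it.** Correct. It may also be tempting to treat quality of life as central to the tolerability claim. Section 1.6.2 measures tolerability by CNS toxicity and radiation necrosis and lists quality of life separately.

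**Deaths.** A reader might infer that the plan ignores visits lost to death and is therefore biased. That would be read from silence. In an illustrative simulation with no quality-of-life effect and an assumed link between quality of life and survival, the survivor-only difference at 12 months was zero with equal survival, and about −0.03 and −0.05 SD for overall-survival hazard ratios of 0.8 and 0.7. Nor would a mixed model remove the problem, because it treats scores after death as merely missing.

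**The size rests on assumptions.** True. At ρ = 0.3 the gain is only about 10%, and normality favours ANCOVA. That is a reason to keep the rank test as sensitivity.

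**Conclusion.** The point holds as a minor one. The between-arm method that section 9.4 names for scales leaves out a baseline score that is scheduled for every patient, and the section ties adjustment to observed imbalance. The cost is precision: a variance factor of 0.91 to 0.51 is forgone for an assumed ρ of 0.3 to 0.7, equal to about 10% to 96% more patients, with 33% at ρ = 0.5. The gain from adjustment exists for any non-zero ρ, but its size depends on a correlation that the protocol does not give. The power figures rest also on the assumed 0.3 SD, normal scores and full completion by survivors.

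The documents do not support a claim of biased quality-of-life results, of a compromised tolerability objective, or of any effect on the primary endpoint or its type I error.

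**What to change.** In section 9.4, make the between-arm analysis of each quality-of-life scale a baseline-adjusted model. Either of these would serve:

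- ANCOVA at each visit, with the baseline score and the two stratification factors (metastasis volume and primary histology); or
- a mixed model for repeated measures with baseline, arm, visit, arm-by-visit and the two stratification factors, which also uses the earlier visits of patients who later drop out.

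Report adjusted differences with confidence intervals, and keep the Wilcoxon-Mann-Whitney test as a sensitivity analysis. Beside each estimate, show the number alive and the number completing in each arm. State that later visits are interpreted conditionally on survival, because the model does not resolve truncation by death.

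The cost is analysis wording and a little more programming, with no new data, visits or patients. The downside is reliance on model assumptions, which the retained rank test covers.

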4.3. Randomization of subjects

Randomization is stratified according to metastasis volume ($< 14.1 \text{ cm}^3$, $\geq 14.1 \text{ cm}^3$) and primary tumor histology (radioresistant histology: melanoma, renal cell carcinoma and sarcoma vs. other). If multiple cerebral metastases are treated in the trial, the total volume of all treated metastases is used for stratification.

Randomization will be performed on patient level.

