Time-to-event data such as time to local progression (TTLP), local progression-free survival (LPFS), and overall survival (OS) will be presented in life tables constructed using the KAPLAN-MEIER method (Kaplan et al. 1958) and compared using the log-rank test (Here, LPFS is defined like TTLP except that death not preceded by local progression will not be censored but counted as an event). If the assumption of "proportional hazards" underlying the Peto log rank test (Peto et al. 1972, Peto et al. 1976) clearly does not apply (Haybittle 1988), Gehan's generalized Wilcoxon test for comparing arbitrarily singly-censored samples will also be used as sensitivity analysis (Gehan 1965), preferably, as modified by Peto and co-workers and Prentice (Peto et al. 1972, Prentice 1978). Prospective stratification and other prognostic strata, if necessary, may be taken into account in further sensitivity analyses (Peto et al. 1976).

TTLP, the primary endpoint of the study, will be described and evaluated in another sensitivity analysis based on the cumulative incidence method (Gray 1988), in which death not associated with local progression will be treated as a competing risk event

Univariate consideration of prognostic factors will be performed by applying the above-mentioned methods accordingly. Multivariate analysis, if required, will be performed using the Cox proportional hazards regression model (Cox 1972).

Further details regarding the statistical analysis will be specified prospectively in a Statistical Analysis Plan before any analyses of treatment efficacy are carried out. As software, SPSS, R, TESTIMATE, and/or SQL will be used for analysis.

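### OS and LPFS are compared by an unadjusted log-rank test, with covariates left to a data-dependent trigger, although GPA and RPA are recorded for every patient at screening

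*Protocol*

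**What the plan says.** Protocol section 5.1.1 and the examination schedule put this among the screening items: "Assessment of RPA and GPA prognostic scores". Section 9 does not name either score again.

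Section 9.4 takes TTLP, LPFS and OS together. They are shown as Kaplan-Meier life tables and "compared using the log-rank test". LPFS differs from TTLP in that death without earlier local progression counts as an event. A stratified log-rank test is laid down only for the primary endpoint, TTLP. The strata come from section 4.3: "Randomization is stratified according to metastasis volume" (total treated volume, cut at 14.1 cm³) and by radioresistant versus other histology.

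The routes to adjustment in section 9.4 are:
- Imbalance: "Sensitivity analyses will be conducted if needed to adjust for relevant imbalances in the study population by appropriate modeling or stratification". Adjusted and unadjusted results are then to be compared.
- Strata: the randomization strata and other prognostic strata may be used in further sensitivity analyses where thought necessary.
- Prognostic factors: a univariate look at them is a firm commitment, but the factors are not named.
- Modelling: "Multivariate analysis, if required, will be performed using the Cox proportional hazards regression model".

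Section 9.4 treats p-values outside the primary test as descriptive. It leaves further detail to a SAP, to be written before any efficacy analysis.

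**The concern.** GPA and RPA are prognostic scores fixed before treatment and available for everyone. Section 9.2 expects that "about half of the patients will be dead at 12-month follow-up", so deaths will be many, and they drive OS and enter LPFS. The randomization strata contain neither score. As written, the main between-arm comparison of OS and LPFS uses neither the scores nor the strata, and a model with covariates appears only on a condition.

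Two things are at stake. First, when patients differ in prognosis and the analysis ignores it, the log-rank test loses power even if the arms are perfectly balanced. A rule that waits for imbalance addresses a different problem and does not restore that power. Second, a trigger that depends on observed imbalance, with covariates not named, makes the choice of model depend on the data. The trial is open (section 2.1), so this leaves some room for selective emphasis.

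**Working it through.** **The plan's own figure.** The protocol gives no power, effect or sample size for OS or LPFS. Its only calculation is for TTLP (section 9.2): 12-month control 65% versus 80%, half the patients dead by 12 months, one-sided 2.5%, 80% power, Lachin-Foulkes.
- Yearly hazards: λc = −ln 0.65 = 0.431, λe = −ln 0.80 = 0.223, mean λ̄ = 0.327; loss rate η = ln 2 = 0.693.
- P(event by 12 months) = λ/(λ+η) × (1 − e^−(λ+η)): 0.2587 (SRS), 0.1461 (FSRT), 0.2050 (at λ̄).
- With s = λ²/P: s₀ = 0.522, sc = 0.717, se = 0.341.
- N = [(1.96√(4s₀) + 0.842√(2sc + 2se)) / (λc − λe)]² = [(2.831 + 1.224)/0.2076]² ≈ 381.5, or 191 per arm. The stated 382 is reproduced.
- Expected events are 191 × (0.2587 + 0.1461) ≈ 77 against the stated 82. That difference has no bearing on this point.

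**Inputs for OS.** From the protocol: 382 patients, 1:1 allocation, about 50% dead at 12 months (applied to the control arm), follow-up to 24 months. Assumed, because the protocol is silent: the OS hazard ratio (HR) and the spread of log hazard explained by the score. All tests are two-sided 5%.

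**Check 1: Cox model with and without a normally distributed score, assumed OS HR 0.72, 3,000 runs per setting.**

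| Log-hazard SD | Power, unadjusted | Power, adjusted | Gain (points) | Average unadjusted HR |
|---|---|---|---|---|
| 0.3 | 72.9% | 76.7% | +3.8 | 0.73 |
| 0.5 | 64.4% | 74.2% | +9.8 | 0.75 |
| 0.7 | 58.3% | 73.6% | +15.3 | 0.76 |

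Two separate repeats at HR 0.72 (2,000 and 1,500 runs per setting) gave +4/+10/+17 and +4/+9/+17. The simulation standard error of one power figure near 70% is √(0.7 × 0.3/1,500) ≈ 1.2 points at 1,500 runs and 0.8 at 3,000.

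**Check 2: smaller OS effects (1,500 runs per setting).** Gains for SD 0.3/0.5/0.7:
- HR 0.80: +2/+6/+10 points.
- HR 0.85: 25→27%, 21→25%, 19→27%, so +2/+4/+8.
- HR 0.90: −1/+3/+2, with power at most 16% either way; this is simulation noise around a very small gain.

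**Check 3: does the imbalance trigger recover the loss?** From the 2,000-run repeat at HR 0.72, keep only trials whose arms differ on the score by less than one standard error, where an imbalance rule would not fire. Power is then 72→75%, 67→78% and 55→72%, a gain of +3/+11/+17. The loss is as large in balanced trials as overall.

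**Check 4: a different method.** Take three equal prognostic classes with hazard ratio h between neighbours, and compare the plain log-rank with a log-rank stratified by class (3,000 runs). The implied log-hazard SD is ln h × √(2/3).

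| h | SD | Treatment HR 0.70: plain → stratified | Treatment HR 0.75: plain → stratified |
|---|---|---|---|
| 1.0 | 0 | 82 → 81% | 65 → 64% |
| 1.5 | 0.33 | 77 → 81% | 62 → 66% |
| 2.0 | 0.57 | 69 → 80% | 51 → 62% |
| 2.5 | 0.75 | 61 → 79% | 45 → 63% |
| 3.0 | 0.90 | 53 → 79% | 35 → 60% |

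At comparable SD this agrees with Check 1. A score with no prognostic value brings no gain and almost no cost. With no treatment effect, both tests reject in 4.8 to 5.5% of trials.

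**The case against.** The strongest reply is that naming covariates for secondary endpoints is ordinary SAP content, and section 9.4 promises a SAP before efficacy is analysed. Silence on the covariate list would indeed be no finding. But the protocol is not silent: it states a rule that adjustment follows observed imbalance or perceived need. A SAP could name covariates and still keep that trigger. The rule is the point, not the missing list.

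The second reply is that nothing confirmatory is harmed. This stands. Only TTLP is tested confirmatorily, and its main test uses the randomization strata. OS and LPFS have descriptive p-values and no power target. Their hazard ratios and intervals will still be read.

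The third reply is that the size rests on assumptions. This also stands. At HR 0.85 to 0.90 the OS comparison is weak with or without the score. A normal, correctly modelled score is a favourable case for a coarse clinical index.

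A reader might go further and infer that the scores enter no planned survival analysis at all. The text does not support that: a univariate prognostic-factor analysis is committed, and adjusted sensitivity analyses and Cox regression are provided for. What is missing is a pre-specified adjusted comparison of the arms. A reader might also take the move from 0.72 to 0.73–0.76 as bias. It is the difference between a conditional and a marginal hazard ratio, and the unadjusted log-rank test remains valid in a randomized trial.

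**Conclusion.** The point holds as a low-cost improvement, not as an error in any stated figure. Section 9.4 compares OS and LPFS without the scores or strata already in hand, and its conditional adjustment neither recovers the lost power nor fixes the model in advance.

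Under assumed OS hazard ratios of 0.72 to 0.90 and a log-hazard SD of 0.3 to 0.7, the OS power gain runs from about 0 to +17 points. The direction is firm if the score is prognostic; the size cannot be settled from the protocol.

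Three further inferences are not supported:
- That GPA is the strongest predictor of death collected. The protocol says only that GPA and RPA are prognostic scores.
- That three quarters of patients will be dead at 24 months. This extends the 12-month figure exponentially (1 − 0.5² = 75%). The Check 1 simulations gave 251 to 261 deaths of 382, or 66 to 68%.
- That brain-metastasis-specific survival loses a similar amount. It depends on cause of death and was not calculated. For LPFS the same mechanism acts through the deaths it counts, but only OS was simulated.

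**What to change.** State in section 9.4, and carry into the SAP, that OS and LPFS are compared by a Cox model with treatment and GPA score, stratified by or adjusted for the two randomization factors (volume, histology), whatever the observed balance. Report it beside the Kaplan-Meier curves and the unadjusted log-rank test. The primary TTLP analysis stays as it is.

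The cost is about one sentence. The data are already collected and no patient procedure changes. The small downside is that the adjusted hazard ratio is conditional on GPA and relies on the form in which GPA enters the model, which is why the unadjusted result should stand next to it. If the SAP already fixes such a model, section 9.4 only needs to be brought into line with it.
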